## **6.7. Study Medication Management**

### **6.7.1. Accountability**

The investigator or designee will maintain an accurate record of the receipt of the study medication as shipped by Aclaris Therapeutics, Inc. (or designee), including the date received and the condition of the study medications. One copy of this receipt will be returned to Aclaris Therapeutics, Inc. (or designee) when the contents of the study medication shipment have been verified and one copy maintained in the study file. In addition, an accurate study medication disposition record will be kept, specifying the amount dispensed for each subject and the date of dispensing. This inventory record will be available for inspection at any time. At the completion of the study, the original inventory record will be available for review by Aclaris Therapeutics, Inc. upon request.

### **6.7.2. Return and disposition of study supplies**

At the completion of the study, all used and unused study medication bottles will be returned to Aclaris Therapeutics, Inc. (or designee) for disposal per Aclaris Therapeutics, Inc. (or designee's) written instructions.

## **6.8. Other Study Supplies**

Aclaris Therapeutics, Inc. will provide:

- Supplies for urine pregnancy tests
- Equipment, supplies and training for taking standardized photographs
- Equipment, supplies and training for capturing ECGs for central reading
- Disposable applicators

## **6.9. Blinding**

### **6.9.1. Verification of blinding**

This study uses an open-label design.

### **6.9.2. Unblinding the study medication**

This is an open-label study.

## **7. STUDY ASSESSMENTS**

The investigator, a designated and appropriately trained staff member (*e.g.*, subinvestigator) or the subject will perform the study assessments according to the schedules noted below.

The same individual should perform the assessments for a given subject throughout the study. If this becomes impossible, an appropriate designee with overlapping experience with the subject and the study should perform the assessments.

Similar lighting conditions and subject positioning should be used for all evaluations for a given subject.

## 7.1. Effectiveness Evaluations

The investigator will identify the affected area(s) at baseline in the source document and eCRF. The affected area is defined as the area of eyebrow hair loss identified at baseline.

### 7.1.1. Clinician's Eyebrow Assessment (CEA)

The CEA is the investigator's assessment of the affected area of the eyebrow(s) at a particular point in time. The investigator should NOT refer to any other assessments to assist with these assessments.

At Visits 1, 2 and 5-11, the investigator or designee will assess the affected area of the eyebrow(s) using the scale below and report the one integer that best describes the amount of eyebrow hair present. If both eyebrows are affected, each eyebrow should be evaluated separately:

#### Clinician's Eyebrow Assessment

Grade	Descriptor
0	No eyebrow hair: No terminal hairs are visible in the affected area(s)
1	A little eyebrow hair: Occasional terminal hairs are visible in the affected area(s)
2	Some eyebrow hair: Numerous terminal hairs are visible in the affected area(s)
3	Most eyebrow hair: Mostly complete eyebrow regrowth with terminal hair in the affected area(s)
4	Full eyebrow hair: Complete eyebrow regrowth with terminal hair in the affected area(s)

At Visit 1 for the subject to be enrolled and at Visit 2 for the subject to continue in the study and to apply study medication to one or both eyebrow(s), he or she must have a CEA grade of 0 in a distinct patch of at least 30% total hair loss in one or both eyebrows. Note: the subject may have multiple patches of eyebrow hair loss, but at least one distinct patch must demonstrate a minimum hair loss of at least 30% (independent of any other patches).

The investigator will record if vellus hair is present (Y/N) in the affected area at Visits 1, 2 and 5-11.

### 7.1.2. Subject's Eyebrow Assessment (SEA)

The SEA is the subject's assessment of the affected area of the eyebrow(s) at a particular point in time. The subject should NOT refer to any other assessments to assist with these assessments.

At Visits 1, 2 and 5-11, the subject will assess the affected area of the eyebrow(s) using the scale below and report the one integer that best describes the amount of eyebrow hair present. If applicable, each eyebrow should be evaluated separately:

#### Subject's Eyebrow Assessment

Grade	Descriptor
0	No eyebrow hair: No thick, coarse hairs are visible in the affected area(s)
1	A little eyebrow hair: A few thick, coarse hairs are visible in the affected area(s)
2	Some eyebrow hair: Numerous thick, coarse hairs are visible in the affected area(s)
3	Most eyebrow hair: The majority of the affected area(s) of the eyebrow is covered in thick, coarse hairs
4	Full eyebrow hair: The affected area(s) of the eyebrow is fully covered in thick, coarse hairs

An investigational staff member will identify the eyebrow to be evaluated to the subject, educate the subject on the SEA scale before each evaluation and direct the subject to assess the affected area of the eyebrow. The staff member should not influence the subject's assessment.

At Visit 1 for the subject to be enrolled and at Visit 2 for the subject to continue in the study and to apply study medication to one or both eyebrows, he or she must have a SEA grade of 0 in at least one eyebrow in a distinct patch of at least 30% total hair loss in one or both eyebrows. Note: the subject may have multiple patches of eyebrow hair loss, but at least one distinct patch must demonstrate a minimum hair loss of at least 30% (independent of any other patches).

The study staff member will report the SEA grade the subject indicates in the source document for each eyebrow. Both the subject and the study staff member must sign/initial the source document to indicate the subject performed the SEA as instructed.

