## **5. SELECTION AND DISPOSITION OF STUDY POPULATION**

### **5.1. Number of Subjects**

Approximately 12 subjects will be enrolled at 1 to 2 sites in the United States.

CONFIDENTIAL  
Page 18 of 57

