#### 6.3.1. Visit 1/ Screening (Week -4 to 0)

At this visit, the investigator or designee will:

1. Review and explain the nature of the study to the subject, obtain the subject's signature on the appropriate approved ICF and provide a signed and dated copy to the subject.
2. Assign a SI to the subject.
3. Confirm the subject meets all inclusion criteria and no exclusion criteria.
4. Collect demographic and medical history information (including alopecia history).
5. Collect concomitant therapies information.
6. Perform a brief physical examination.
7. Measure vital signs (including Height & Weight at this visit only).
8. Conduct an ECG.
9. Send patient for clinical laboratory tests including serum pregnancy test (if subject is WOCBP).
10. Identify the affected areas of eyebrow(s). Affected area is defined as the area of the eyebrow hair loss identified at baseline.
11. Perform a Clinician Eyebrow Assessment (CEA); a grade of 0 is required for at least one eyebrow with at least 30% eyebrow loss for the subject to continue in the study. Note: the subject may have multiple patches of eyebrow hair loss, but at least one distinct patch must demonstrate a minimum hair loss of at least 30% (independent of any other patches).
12. Have the subject complete a Subject Eyebrow Assessment (SEA); a grade of 0 is required for at least one eyebrow with at least 30% eyebrow loss for the subject to continue in the study. Note: the subject may have multiple patches of eyebrow hair loss, but at least one distinct patch must demonstrate a minimum hair loss of at least 30% (independent of any other patches).
13. Review the study instructions with the subject.
14. Schedule Visit 2 as appropriate.

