### 6.3.2. Visit 2/ Baseline (Day 1)

This visit must occur within 28 days after Visit 1.

Subsequent study visit dates must be scheduled based on the date of Visit 2.

This visit may not occur before the investigator reviews the Visit 1 clinical laboratory test results for all the measured analytes. For the subject to continue in the study all clinical laboratory test results must be within the range of normal for the laboratory or, if there are any abnormal results, they must be defined as not clinically significant (NCS) by the investigator. For WOCBP, the serum pregnancy test from Visit 1 must be negative for a subject to continue in the study.

The investigator must review the evaluator's interpretation of each subject's Visit 1 ECG prior to Baseline/Visit 2 and comment on the clinical significance of any result that is defined by the evaluator as abnormal. The subject must not continue in the study and apply study medication, if the Visit 1 ECG meets any of the Criteria in Exclusion Criterion 18).

At this visit, the investigator or designee will perform the following procedures PRIOR TO APPLICATION OF STUDY MEDICATION:

1. Subject should have clinical laboratory tests performed at the local laboratory on the same day as the visit.
2. Query the subject in a non-directive manner about any changes in her/his health since the previous visit and report changes on the appropriate form.
3. Query the subject about any changes in her/his concomitant therapies since the previous visit and report changes on the appropriate form.
4. Confirm the subject meets all inclusion criteria and no exclusion criteria.
5. Confirm the subject continues to comply with all study restrictions, is eligible to continue in the study and has followed all study instructions.
6. Measure vital signs.
7. Perform a urine pregnancy test for WOCBP; results must be negative for the subject to apply the first dose of study medication.
8. The investigator or designee will perform a CEA; a CEA grade of 0 in a distinct patch of at least 30% total unilateral eyebrow hair loss is required for the subject to apply the first dose of study medication. Note: the subject may have multiple patches of eyebrow hair loss, but at least one distinct patch must demonstrate a minimum hair loss of at least 30% (independent of any other patches).
9. Confirm subject is eligible to apply the first dose of study medication.

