#### **6.3.4. Visit 10 (Week 24)**

This visit must occur 24 weeks ( $\pm 4$  days) after Visit 2.

At this visit, the investigator or designee will perform the following procedures:

1. Query the subject in a non-directive manner about any changes in her/his health since the previous visit and report all AEs on the appropriate form.
2. Query the subject about any changes in her/his concomitant therapies since the previous visit and report changes on the appropriate form.
3. Confirm the subject continues to comply with all study restrictions and has followed all study instructions.
4. Measure vital signs.
5. Conduct an ECG.
6. Confirm subject had clinical laboratory tests prior to the visit (on the same day).
7. Perform a urine pregnancy test for WOCBP.
8. Have the subject perform a LTA.
9. The investigator or designee will perform a LTA.
10. The investigator or designee will perform the CEA.
11. Have the subject complete the SEA.
12. Have the subject complete the SES.
13. Collect all study medication.
14. Take standardized photographs.
15. Review the study instructions with the subject.
16. Schedule the next visit as appropriate.

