**Subject's Eyebrow Satisfaction**

Grade	Descriptor
1	Extremely satisfied
2	Moderately satisfied
3	A little satisfied
4	Neither satisfied or dissatisfied
5	A little dissatisfied
6	Moderately dissatisfied
7	Extremely dissatisfied

An investigational staff member will identify the affected eyebrow to be evaluated to the subject, educate the subject on the SES scale before each evaluation and direct the subject to assess the eyebrow. The staff member should not influence the subject's assessment.

The study staff member will report the SES grade the subject indicates for each eyebrow in the source document. Both the subject and the study staff member must sign/initial the source document to indicate the subject performed the SES as instructed.

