### **Local Tolerability Assessment – Burning**

Grade	Descriptor
0	Clear: No burning
1	Mild: Slight warmth, not bothersome
2	Moderate: Definite warmth, slightly bothersome
3	Severe: Intense feeling of heat, bothersome and/or uncomfortable

Follow these steps to complete the LTA for each symptom by a subject:

- An investigational center staff member, other than the evaluating investigator, will show the appropriate LTA symptom grading scale to the subject and instruct the subject on the time interval to be considered.
- The staff member should not give any opinion on the meaning of the LTA descriptors.
- The subject should verbally indicate the appropriate grade for each eyebrow for each symptom and the staff member will report the grade in the source document.
- Both the subject and the staff member must sign/initial the source document to indicate the subject performed the LTA for symptoms as instructed.
- The staff member must not influence the subject's assessment.

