## **10.2. Sample Size**

This is the first US-based study with topical ATI-50002 Topical Solution for the treatment of eyebrow loss due to AA, AU/AT. No formal power calculations will be performed.

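### The visit lists and rating instructions do not protect the subject's SEA (and, less directly, the SES) from the clinician's CEA as the protocol protects the LTA symptoms, and the Visit 2 lists confirm eligibility before the SEA that eligibility requires

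*Combined protocol and SAP*

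**What the plan says.** **Who administers the subject scales.** Section 7.1.2 (SEA) states: "An investigational staff member will identify the eyebrow to be evaluated to the subject, educate the subject on the SEA scale before each evaluation". Section 7.1.3 uses the same arrangement for the SES and adds: "The study staff member will report the SES grade the subject indicates for each eyebrow in the source document". Neither section excludes the person who graded the CEA. Sections 7 and 7.1.1 let the investigator or a trained designee do the CEA.

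**What partial protection exists.** Both sections tell the subject to rate without consulting other assessments and tell staff not to influence the rating. Both also require subject and staff to sign or initial that the rating was done as instructed.

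**What the LTA has in addition.** For subject-rated stinging and burning, section 7.2.5 states: "An investigational center staff member, other than the evaluating investigator, will show the appropriate LTA symptom grading scale to the subject". It also bars that person from offering a view on what the descriptors mean.

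**Order.** At Visit 1, step 11 is "Perform a Clinician Eyebrow Assessment (CEA); a grade of 0 is required for at least one eyebrow with at least 30% eyebrow loss", and the SEA is step 12. At Visit 10 the CEA is step 10, and step 11 is "Have the subject complete the SEA". At Visit 2 the CEA is step 8 of the pre-application list and step 9 is "Confirm subject is eligible to apply the first dose of study medication". Step 10 discharges those who are not eligible, and the SEA opens the next list.

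**Use.** Section 10.1 names three efficacy parameters: mean change from Visit 2 to Visit 10 in CEA, SEA and SES.

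**The concern.** This is a single-arm, open-label study: "Approximately 12 subjects will be enrolled at 1 to 2 sites in the United States". With no control group and no planned scoring of the photographs, the SEA is the only other scored view of how much hair is present. A reader will naturally take similar CEA and SEA changes as two observers agreeing. That inference needs the subject to have rated without cues from the clinician.

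CEA and SEA use the same five headline labels for grades 0 to 4, so a CEA grade spoken or implied during the examination could be repeated directly as the SEA. The protocol has a stronger procedure for keeping the clinician away from a subject rating, in the LTA, but applies it to tolerability symptoms and not to the efficacy scales. No reason is given.

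Visit 2 matters most because it is the baseline for every change score. The lists there treat the subject as eligible before one of the eligibility assessments has been done.

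**Working it through.** The plan gives no figure to reproduce: "No formal power calculations will be performed". The check sets the step numbers of sections 6.3.1 to 6.3.5 side by side.

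| Visit | CEA | SEA | SES | LTA, subject then investigator |
|---|---|---|---|---|
| 1 | 11 | 12 | not done | not done |
| 2 | 8, first list | 1, second list | 2, second list | 3 then 4 before application; 10 then 20 minutes after |
| 5-9 | 8 | 9 | 11, Visit 7 only | 6 then 7 |
| 10 | 10 | 11 | 12 | 8 then 9 |
| 11 | 11 | 12 | 13 | 9 then 10 |

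Visits 3 and 4 have the LTA only, at steps 6 and 7.

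Counts:
- CEA before SEA: Visits 1, 2, 5, 6, 7, 8, 9, 10, 11, which is 9 of 9.
- CEA before SES: Visits 2, 7, 10, 11, which is 4 of 4.
- Subject LTA before investigator LTA: Visits 2 to 11, which is 10 of 10, including both Visit 2 time points.

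**Administrator.** The LTA excludes the evaluating investigator. The SEA and SES do not exclude the CEA rater. Since the CEA may be done by a staff designee, one person may grade the CEA, teach the SEA scale and write down the subject's answer without departing from the protocol.

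**Visit 2.** Inclusion criterion 4 requires an SEA of 0 in at least one eyebrow.
1. Step 4 of the first list confirms that all inclusion criteria are met, before either eyebrow assessment that day.
2. Step 8 is the CEA, step 9 confirms eligibility and step 10 discharges the ineligible.
3. The second list is restricted to subjects already found eligible, yet its step 1 is an SEA that must be 0 before the first application. No discharge step follows it.

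The lists therefore contradict each other on when eligibility is settled. A subject who reaches the SEA has passed step 10 and can infer that the CEA requirement was met.

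**Scale only.** If one score per subject is averaged over 12 subjects, one subject moving one grade shifts the mean SEA by 1/12 = 0.083, and four such subjects shift it by 4/12 = 0.33. The four is arbitrary. The analysis set is the per-protocol population, which may be smaller than 12, and eyebrows are rated separately. These figures show what a given shift would do. They do not estimate how many subjects would shift.

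**The case against.** The strongest reply is that nothing says the CEA grade is spoken or shown to the subject. The instructions in 7.1.2 and 7.1.3 and the double sign-off point the other way. This stands. A reader might infer that the subject scores are in fact dependent on the clinician's grade, but the documents support only that independence is not fully protected by procedure.

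Second, list order need not be the order in time. Visit 1 step 3 confirms all criteria before the ECG, laboratory tests and eyebrow grades that decide them. Where sequence matters, the protocol sets it explicitly, as with the timed LTA and the pre-application photographs. This stands for every visit except Visit 2, where the second list is conditional on the outcome of the first.

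Third, the LTA is an imperfect comparator. Subject and investigator rate different items there, and the subject-first order is never called a safeguard. The separate-administrator rule is also missing from the SEA and SES, which is different from being reversed. Both points stand, but a workable rule still exists in the same protocol and was not carried over.

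Fourth, standardized photographs are taken at Visits 2 and 5-11, so it would be too strong to call the SEA and SES the only check on the CEA. No photographic scoring is planned, but a record exists. The shared-label route also does not apply to the SES, a 1-to-7 satisfaction scale running the other way. Any effect there would be less direct.

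Fifth, the motive to report 0 at Visit 2 comes from the eligibility rule and would survive reordering. This stands.

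Sixth, putting the subject first could expose the CEA to the subject's answer. This is a fair warning, and it is why non-disclosure has to run both ways.

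Finally, section 10.1 plans separate descriptive summaries with no analysis of agreement. That lowers the stakes but does not stop readers from comparing the two scales.

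**Conclusion.** The concern holds in a limited form. The protocol gives the SEA, and less directly the SES at Visits 2, 7, 10 and 11, weaker procedural protection from the CEA than it gives the LTA symptoms. The Visit 2 lists are internally inconsistent. Agreement between CEA and SEA therefore cannot be read as fully independent confirmation of regrowth.

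The size of any bias is not estimable from the documents. It depends on whether sites follow the listed order, whether one person fills both roles, and whether the CEA grade becomes known to the subject. The documents settle none of these, apart from the order implied by the two-list layout at Visit 2. No sample-size or power figure is affected. The change is worth making because it is cheap, but the point does not invalidate the planned summaries.

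**What to change.** 1. In sections 6.3.1 to 6.3.5, list the SEA, and the SES where scheduled, before the CEA.
2. Reconcile the two Visit 2 lists so that the SEA precedes the eligibility confirmation and discharge steps.
3. Carry the separate-administrator rule of 7.2.5 into 7.1.2 and 7.1.3: SEA and SES are administered and recorded by staff other than the CEA rater.
4. State that neither the CEA grade nor the SEA or SES grade is disclosed to the other rater until both are recorded.

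The cost is a few edited lines and minor visit logistics. The LTA already requires a second staff member at Visits 2-11, so no staff are added at Visits 2 and 5-11, which include every score used in the change from baseline. Visit 1 has no LTA and may need a second person for the screening SEA. Reordering removes the cue at Visit 2 but not the incentive that the eligibility rule itself creates.

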### 7.1.3. Subject Eyebrow Satisfaction (SES)

The SES is the subject's assessment of her/his satisfaction with the status of the affected eyebrow(s), relative to the amount of hair present, at a particular point in time. The subject should NOT refer to any other assessments to assist with these assessments.

At Visits 2, 7, 10 and 11, the subject will assess the affected eyebrow(s) using the scale below and report the one integer that best describes her/his satisfaction with the status of the affected eyebrow(s). If both eyebrows are affected, each eyebrow should be evaluated separately:

**Subject's Eyebrow Satisfaction**

Grade	Descriptor
1	Extremely satisfied
2	Moderately satisfied
3	A little satisfied
4	Neither satisfied or dissatisfied
5	A little dissatisfied
6	Moderately dissatisfied
7	Extremely dissatisfied

An investigational staff member will identify the affected eyebrow to be evaluated to the subject, educate the subject on the SES scale before each evaluation and direct the subject to assess the eyebrow. The staff member should not influence the subject's assessment.

The study staff member will report the SES grade the subject indicates for each eyebrow in the source document. Both the subject and the study staff member must sign/initial the source document to indicate the subject performed the SES as instructed.

